12. PHARMACOKINETIC ASSESSMENTS

Plasma concentration levels of apilimod and the active metabolites will be measured in the dose-escalation and dose-expansion stages at each of the specified time points; Table 8: Schedule of Assessments (LAM-002A Continuous Monotherapy Administration), Table 9: Schedule of Assessments (LAM-002A Intermittent Monotherapy Administration), Table 10: Schedule of Assessments (LAM-002A/Rituximab Combination Therapy), and Table 11: Schedule of Assessments (LAM-002A/Atezolizumab Combination Therapy) in Section 8.7 The analytical laboratory will measure plasma concentrations of apilimod using a validated analytic method. PK parameters that will be estimated on Day 1 and Day 8 using standard non-compartmental methods as follows will include: C_{max}, t_{max}, AUC_{0-t}, AUC_τ; t_{1/2}, trough concentrations on Days 8 and 15, and a comparison of AUC_{0-t} from Days 1 and 8 or Days 1 and Day 10 (as appropriate); additional parameters may be determined based on the available data. Accumulation will be assessed by calculating the Day 15/Day 1 accumulation ratios I for C_{max} and AUC when comparing Day 8 to Day 1 for all continuous LAM-002A regimens (whether given as monotherapy or in combination) or when comparing Day 10 to Day 1 for the intermittent LAM-002A regimen. Dose proportionality for C_{max} and AUC_{0-t} will be assessed by applying an appropriate power model to the data. Descriptive statistics of PK parameters will include minimum, maximum, mean, standard deviation, percent coefficient of variation (%CV), and range.

Metabolite concentrations at the time points indicated in Table 13. All subjects must participate in PK assessments. Fasting status must be recorded at the time of each PK blood draw.

Protocol: LAM-002A-NHL-CLN01

Version 9, 18 Feb 2020

Table 13: Pharmacokinetic Sampling Time Points

Sample	Study Day	PK Sampling Time Points ^a
1 ^b	1	Pre-dose (within 30 min prior to dose of LAM-002A)
2	1	0.5 hour (± 10 min) after dosing with LAM-002A
3	1	1 hour (± 10 min) after dosing with LAM-002A
4	1	2 hours (± 10 min) after dosing with LAM-002A
5	1	4 hours (± 10 min) after dosing with LAM-002A
6	1	6 hours (± 10 min) after dosing with LAM-002A
7	1	8 hours (± 10 min) after dosing with LAM-002A
8 ^b	8 or 10 ^c	Pre-dose (within 30 min prior to dose of LAM-002A)
9	8 or 10 ^c	0.5 hour (± 10 min) after dosing with LAM-002A
10	8 or 10°	1 hour (± 10 min) after dosing with LAM-002A
11	8 or 10°	2 hours (± 10 min) after dosing with LAM-002A
12	8 or 10°	4 hours (± 10 min) after dosing with LAM-002A
13	8 or 10 ^c	6 hours (± 10 min) after dosing with LAM-002A
14	8 or 10 ^c	8 hours (± 10 min) after dosing with LAM-002A
15 ^b	15	Pre-dose (within 30 min prior to dose of LAM-002A)

^a Applies to first dose of the day

Abbreviations: min: Minutes; PK: Pharmacokinetic

Comprehensive information on blood sample acquisition, handling, storage and sample shipments can be found in the pharmacokinetic laboratory manual.

On Cycle 1 Day 1, and Cycle 1 Day 8 the dose of LAM-002A should be orally administered (a minimum fasting state of 6 to 8 hours) by staff in the clinic immediately after the collection of the biomarker samples and after the collection of the first PK sample. Subjects are allowed to eat after PK Sample #4 (hour 2) has been collected. Subjects may consume clear liquids during fasting periods.

On Cycle 1 Day 15, the dose of LAM-002A should be orally administered (a minimum fasting state of 6 to 8 hours) by staff in the clinic immediately after collection of the pre-dose PK and biomarker samples.

In addition, PK samples may be collected, if possible and deemed appropriate by the Investigator and Sponsor, whenever a subject has a study treatment related SAE or QTc > 500 msec.

^b Dosing with LAM-002A should occur after the PK sample has been drawn.

^c Sampling to be performed on Day 8 for all continuous LAM-002A regimens (whether given as monotherapy or in combination) or on Day 10 for the intermittent LAM-002A dosing regimen.

Version 9, 18 Feb 2020

Section 13. BIOMARKER ASSESSMENTS

Changes: Biomarkers were clarified and updated consistent with emerging data and methods and the modified study therapy plan.

13. BIOMARKER ASSESSMENTS

Plasma Blood smears will be obtained for pharmacodynamics biomarker analysis on C1D1, and C1D15, and at the EOT visit 8 as follows: pre dose, 4 and 8 hours post first dose of the day and C1D15 pre dose only. Samples will be analyzed for circulating tumor DNA to measure tumor burden and mutational changes. PIK five inhibition as determined by the extent of vacuolation by microscopy.

Plasma pharmacodynamic samples will also be collected for determination of plasma apilimod and active metabolite activity at the PK time points indicated in Table 13. The plasma will be used in an ex vivo cathepsin activity assay or equivalent to determine level of PIKfyve inhibition.

Plasma will also be collected for evaluation of circulating cytokines (including IL-12 and IL-23) predose on each of Cycle 1 Day 1, Cycle 1 Day 8, and Cycle 1 Day 15 and at the EOT visit. Samples will be analyzed using appropriate □mmune-detection assays.

For all subjects, PBMCs/B cells will be collected on during the prescreening period, Cycle 1, Day 1 pre-treatment; on Cycle 1, Day 1 at 8 hours post-dose; and on Cycle 1, Day 8 at 8 hours post-dose for determination of changes in gene expression that may predict or correlate with anti-lymphoma activity and/or pharmacodynamic activity and will also serve as normal-tissue controls for gene mutation studies in tumors.

For subjects with NHL, archival tissue from the most recent available biopsy or surgery or fresh tumor tissue (preferred) must be obtained pretreatment. Alternatively, cells from a bone marrow aspirate may be obtained in subjects with bone marrow involvement due to NHL (>50% NHL cells). For subjects undergoing a biopsy, adequate tumor tissue should be acquired via excisional biopsy, incisional biopsy or core needle biopsy (e.g., ≥ 3 passes using a 16-gauge core needle). Tissue will be submitted for evaluation of the percentage of tumor cells and analysis of genetic alterations and/or gene expression that may predict anti-lymphoma activity and/or pharmacodynamics activity. In addition, tumor may be evaluated for known prognostic characteristics (e.g., for DLBCL: ABC or GCB subtype; expression of BCL2, BCL6, Ki-67, CD20, and MYC; other mutational status), for PDL1 status, and for immune infiltration.

Subjects with CLL/SLL must provide either a fresh blood sample containing circulating tumor cells or a bone marrow aspirate sample pretreatment. Tissue will be submitted for evaluation of the percentage of tumor cells and analysis of genetic alterations and/or gene expression that may predict anticancer activity and/or pharmacodynamic activity. In addition, for subjects with CLL/SLL, the sponsor may arrange for a portion of the sample to be evaluated at a sponsor-specified laboratory for known prognostic markers (e.g., quantitative immunoglobulins, FISH panel [chromosome 11q deletion, 13q deletion, 17p deletion and 12 trisomy], DNA mutational analysis for p53, IgHV [including IgHV3-21], and other genes of interest in CLL [e.g., Notch]; flow cytometry [for CD5, CD10, CD11c, CD19, CD20, CD23, CD38, CD45, kappa and lambda light chains and ZAP-70], and/or β2-microglobulin).

Version 9, 18 Feb 2020

A saliva sample will be obtained on Cycle 1 Day 1 during Screening as a normal-tissue control for gene mutation studies in tumors.

Comprehensive information on tissue acquisition, handling, storage and sample shipments can be found in the biomarker sample process documents.

Section 14. STATISTICS

Changes: The Stage 1 dose-ranging approach and a statistical basis for the planned Stage 2 cohort sizes were provided. A method for continuous reassessment of safety created a framework for risk assessments associated with the investigational combination therapies to be explored in the study. This safety method complemented the restrictions on the pace of Stage 2 combination therapy enrollment detailed in Section 6.1.3 of the protocol.

14.1. Determination of Sample Size

14.1.1. Stage 1 (Dose Escalation)

The planned sample size for the dose-escalation is not based on a specific statistical hypothesis but on experience in the conduct of similar trials in subjects with cancer.

In the dose escalation, the cohort sizes of 3 to 6 subjects allow evaluation of regimen safety using a standard definition of MTD (ie, a starting dose associated with DLT in <33% of subjects during the first cycle of therapy). Based on the planned 3+3 dose-escalation scheme, Table 14 shows the probability of escalating to the next dose level or proceeding to the next stage, based on the true rate of DLT at the current dose level.

Table 14: Statistical Basis for 3+3 Dose-Escalation Paradigm

True Incidence of DLT	Probability of Escalating
10%	0.91
20%	0.71
30%	0.49
40%	0.31
50%	0.17
60%	0.08

Abbreviation: DLT=dose-limiting toxicity

Thus, if the true underlying proportion of DLT is low (eg, $\leq 10\%$ at the current dose level, there is a high probability (≥ 0.91) of dose escalation to the next dose level. Conversely, if the true underlying proportion of DLT is high (eg, $\geq 60\%$) at the current dose level, there is a low probability (≤ 0.08) of escalation to the next dose level.

14.1.2. Stage 2 (Cohort Expansion)

As indicated in Section 6.1.2, expansion cohorts of 6 subjects will be accrued. Enrollment of 6 subjects per cohort offers the opportunity to determine if there is any antitumor activity sufficient to warrant further development in the selected tumor types. An ORR of \geq 35% is considered of potential interest in each of the selected indications. If 0/6 subjects in a cohort experience an objective response, then a population ORR of \geq 35% for that cancer can be excluded with > 90% certainty (1-sided exact binomial 90% CI upper bound = 32%).

Version 9, 18 Feb 2020

Experience indicates the rates of discontinuations from rituximab or atezolizumab therapy are < 5% (Genentech 2016, Genentech 2017). A rate of AE discontinuations of therapy due to adverse events of \geq 25% in the 2 combination therapy groups of LAM-002A/rituximab (N = 12) or LAM-002A/atezolizumab (N = 12) would suggest a potential adverse interaction among the components of the combination therapy. Sequential Pocock-type boundaries will be used to continuously monitor the rate of AE discontinuations and to test the null hypothesis, after each subject, that the event rate is \geq 0.25 using a 1-sided significance test of \sim 0.05. AE discontinuation rates will be considered excessive if the following n/N values are observed: -/1, -/2, 3/3, 3/4, 4/5, 4/6, 5/7, 5/8, 5/9, 6/10, 6/11, 7/12. With this method, the probability of detecting an AE discontinuation safety signal ranges from 0.091 to >0.820 for true discontinuation rates of 25% to \geq 60%. If excessive levels of AE discontinuation are observed, the sponsor, working in collaboration with the cooperating companies and investigators, will take appropriate actions (eg, continuation of the cohort with modifications in design or monitoring plan, interruption of cohort accrual, cohort therapy discontinuation).

This Phase 1 trial is being conducted primarily to assess the safety and tolerability of LAM 002A (apilimod dimesylate capsules) when administered in subjects with relapsed or refractory B cell NHL and to determine the MTD and RP2D of LAM 002A. No formal sample size estimation was performed. The choice of the number of subjects was based on the standard 3 + 3 design that is commonly used in Phase 1 trials of anti-cancer investigational drugs. For the Dose Escalation Stage of the study, the maximum sample size will be approximately 60 subjects if 6 subjects are assigned to each of the 9 potential dose levels and an additional 6 patients are accrued at the RP2D. However, additional subjects may be added if exploration of intermediate dose level(s) of LAM 002A is warranted.

Up to 45 additional evaluable subjects (3 cohorts of 15 subjects) may be enrolled at the RP2D and schedule in the Expansion Stage of the study. The safety population will consist of all subjects receiving at least 1 dose of LAM 002A. The assessment of DLT and MTD will involve only those subjects completing the first cycle of therapy, unless the subject discontinuation in first cycle was due to a DLT.

Section 21. STUDY DISCONTINUATION

Change: This section was added to separate it from Sections 6.11 and 6.12, which relate to duration of therapy and discontinuation of participation for individual subjects.

12. STUDY DISCONTINUATION

Both the investigator and LAM reserve the right to terminate the study at any time. Should this be necessary, both parties will arrange discontinuation procedures. The investigator will be responsible for notifying the relevant study center IRB. LAM will be responsible for notifying the appropriate regulatory authorities. In terminating the study, the investigator and LAM will assure that adequate consideration is given to the protection of the subjects' interests. As directed by LAM, all study materials must be collected and all eCRFs completed to the greatest extent possible.

Version 9, 18 Feb 2020

Section 22. LIST OF REFERENCES

Change: The reference list was updated to include additional relevant references.

Change: The protocol was modified to permit evaluation of single-agent LAM-002A or the LAM-002A/rituximab combination in additional patients with FL. Use of either intravenously administered rituximab or subcutaneously administered rituximab hyaluronidase human was permitted.

Once the MTD and/or recommended phase 2 dose (RP2D) and schedule is determined, the study will enter the expansion stage, in which cohorts of subjects will be accrued in order to obtain additional information on safety, tolerability, preliminary anti-tumor activity, PK, and pharmacodynamic data at the RP2D and schedule when LAM-002A is administered alone or in combination with rituximab/rituximab hyaluronidase or atezolizumab. Expansion-stage cohorts will comprise groups of subjects with specific types of previously treated, relapsed, progressive, and measurable NHL who will receive LAM-002A monotherapy or LAM-002A-containing combination therapy as shown in Table 2. For both monotherapy and combination cohorts, the starting dose of LAM-002A will be 125 mg BID administered continuously.

Version 9, 18 Feb 2020

Table 2: Expansion Stage Disease Types and Therapies

Cohort Number	NHL Type	Investigational Drug	Combination Drug	Evaluable Subjects, n
1	FL	LAM-002A		6 Up to ~20
2	MZL	LAM-002A		6
3	DLBCL-GCB	LAM-002A		6
4	DLBCL-ABC	LAM-002A		6
5	FL or MZL	LAM-002A	Rituximab or rituximab hyaluronidase human	6 Up to ~20 with FL
6	DLBCL-GCB or DLBCL-ABC	LAM-002A	Rituximab or rituximab hyaluronidase human	6
7	FL or MZL	LAM-002A	Atezolizumab	6
8	DLBCL-GCB or DLBCL-ABC	LAM-002A	Atezolizumab	6

Abbreviations: ABC: activated B-cell (subtype); DLBCL: diffuse large B-cell lymphoma; FL: follicular lymphoma; GCB: germinal center B-cell (subtype); MZL: marginal zone lymphoma; NHL: non-Hodgkin lymphoma

Section 6.2 Number of Subjects

Change: Information regarding the total potential accrual to the study was updated consistent with modifications to the protocol to evaluate single-agent LAM-002A or the LAM-002A/rituximab combination in additional patients with FL.

As many as $\underline{145}$ $\underline{110}$ subjects will be enrolled, assuming that:

- In the dose-escalation stage of the study, the total number of subjects will depend upon the numbers of subjects accrued to each dose level and the number of dose levels evaluated. If 6 subjects are enrolled at all open starting dose levels (Dose Levels 5, 6, 7, and 8) and 6 additional subjects are enrolled at the MTD or RD, as many as 30 subjects could be enrolled. To allow for the possibility that some subjects may not be fully evaluable for DLT or that an intermediate dose level might be evaluated, up to ~45 subjects may be enrolled.
- In the expansion stage of the study, if all 8 potential expansion cohorts of 6 evaluable subjects are accrued, as many as ~7648 subjects could be enrolled. To allow for the possibility that some subjects may not be fully evaluable for efficacy or to establish bounds on efficacy estimates with greater confidence, up to ~65_100 subjects may be enrolled.

Section 6.8.2.2 In-Clinic LAM-002A Administrations

Change: To 3rd paragraph only: Use of either intravenously administered rituximab or subcutaneously administered rituximab hyaluronidase human was permitted.

When given as a component of combination therapy with rituximab, LAM-002A will be started on Cycle 1 Day 1 with a BID schedule. LAM-002A will be administered after administration of premedications (see Section 6.8.3.1) and ~15 to 30 minutes prior to the start of the initial rituximab infusion. On Cycle 1 Day 8, the morning dose of LAM-002A will be administered

Version 9, 18 Feb 2020

after premedications (see Section 6.8.3.1) and ~15 to 30 minutes prior to the rituximab infusion/injection.

Section 6.8.3 Rituximab or Rituximab/Hyaluronidase Human

Change: Use of either intravenously administered rituximab or subcutaneously administered rituximab hyaluronidase human was permitted. Relevant changes were made to provide necessary dosing and administration information.

6.8.3.1 Premedications

In accordance with rituximab/rituximab hyaluronidase human prescribing information (Genentech 2016, Genentech 2018), subjects should be premedicated with an antipyretic and an antihistamine to reduce the incidence and severity of infusion/injection reactions. A recommended regimen is diphenhydramine, 25 mg orally, and acetaminophen (paracetamol), 650 mg orally, both given ~30 minutes prior to each rituximab administration. Intravenous corticosteroids may also be administered as a premedication. Local practices and guidelines may be followed.

6.8.3.2 Rituximab Administration

Based on past experience with this regimen (Ghielmini 2004, Martinelli 2010), rituximab will be administered intravenously or rituximab/hyaluronidase human will be administered subcutaneously in the clinic for a total of 8 infusions treatments:

Intravenous rituximab (Rituxan®)

- Four induction infusions of 375 mg/m² will be administered weekly on Cycle 1 Day 1, Cycle 1 Day 8, Cycle 1 Day 15, and Cycle 1 Day 22.
- Four subsequent maintenance infusions of 375 mg/m² will be administered every 8 weeks on Cycle 4 Day 1, Cycle 6 Day 1, Cycle 8 Day 1, and Cycle 10 Day 1.

Subcutaneous rituximab (rituximab/hyaluronidase human; Rituxan Hycela®)

- An initial dose of 375 mg/mg² will be administered intravenously on Cycle 1 Day1.
- Three subcutaneous injections of 1,400 mg/23,400 Units (1,400 mg rituximab and 23,400 Units hyaluronidase human) will be administered weekly on Cycle 1 Day 8, Cycle 1 Day 15, and Cycle 1 Day 22.
- Four subsequent maintenance subcutaneous injections of 1,400 mg/23,400 Units (1,400 mg rituximab and 23,400 Units hyaluronidase human) will be administered every 8 weeks on Cycle 4 Day 1, Cycle 6 Day 1, Cycle 8 Day 1, and Cycle 10 Day 1.

The dose for each infusion will be 375 mg/m² of body surface area. The dose calculation of body surface area for infused rituximab will be based on the subject's height and actual body weight prior to therapy. Once established based on the pretreatment body weight, the total dose of rituximab for the subject should not be altered during therapy based on fluctuations in body weight unless required by institutional policy.

Clinical Study Report
16.1 Study Information
Protocol: LAM-002A-NHL-CLN01

Version 9, 18 Feb 2020

At Cycle 1 Day 1, ~30 minutes after administration of the required antipyretic and antihistamine premedications and ~15 to 30 minutes after administration of the first dose of LAM-002A, the first infusion of rituximab will be administered via an infusion pump. For the initial infusion, the recommended infusion rate is 50 mg/hour. In the absence of infusion toxicity, the infusion rate can be increased in 50-mg/hour increments every 30 minutes, to a maximum of 400 mg/hour.

For subsequent rituximab infusions, the required antipyretic and antihistamine premedications will be given and the rituximab will be infused via an infusion pump. For these infusions, the infusion can be initiated at 100 mg/hour. In the absence of infusion toxicity, the infusion rate can be increased in 100-mg/hour increments every 30 minutes, to a maximum of 400 mg/hour. Alternatively, for subjects who tolerate the first infusion with Grade \leq 3 infusion toxicity, subsequent infusions can be administered over a planned infusion time of 90 minutes, with \sim 20% of the total dose administered in the first 30 minutes and the remaining 80% of the total protein dose administered in the subsequent 60 minutes (Dakhil 2014, Genentech 2016).

For subsequent rituximab/hyaluronidase human injections, the required antipyretic and antihistamine premedications will be given and the rituximab/hyaluronidase human will be injected into the subcutaneous tissue of the abdomen over ~5 minutes. Areas where the skin is red, bruised, tender or hard, or areas where there are moles or scars should be avoided. No data are available on performing the injection at other sites of the body. If administration of rituximab/hyaluronidase human is interrupted, drug administration can continue at the same site or at a different site but restricted to the abdomen. Patients should be observed for >15 minutes following the completion of injection. During treatment with rituximab/hyaluronidase human, do not administer other medications for subcutaneous use at the same sites.

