6.8.3.2. Rituximab Administration

Based on past experience with this regimen (Ghielmini 2004, Martinelli 2010), rituximab will be administered intravenously in the clinic for a total of 8 infusions:

- Four induction infusions will be administered weekly on Cycle 1 Day 1, Cycle 1 Day 8, Cycle 1 Day 15, and Cycle 1 Day 22.
- Four subsequent maintenance infusions will be administered every 8 weeks on Cycle 4 Day 1, Cycle 6 Day 1, Cycle 8 Day 1, and Cycle 10 Day 1.

The dose for each infusion will be 375 mg/m² of body surface area. The dose calculation of body surface area will be based on the subject's height and actual body weight prior to therapy. Once established based on the pretreatment body weight, the total dose of rituximab for the subject should not be altered during therapy based on fluctuations in body weight unless required by institutional policy.

At Cycle 1 Day 1, ~30 minutes after administration of the required antipyretic and antihistamine premedications and ~15 to 30 minutes after administration of the first dose of LAM-002A, the first infusion of rituximab will be administered via an infusion pump. For the initial infusion, the recommended infusion rate is 50 mg/hour. In the absence of infusion toxicity, the infusion rate can be increased in 50-mg/hour increments every 30 minutes, to a maximum of 400 mg/hour.

For subsequent infusions, the required antipyretic and antihistamine premedications will be given and the rituximab will be infused via an infusion pump. For these infusions, the infusion can be initiated at 100 mg/hour. In the absence of infusion toxicity, the infusion rate can be increased in 100-mg/hour increments every 30 minutes, to a maximum of 400 mg/hour. Alternatively, for subjects who tolerate the first infusion with Grade \leq 3 infusion toxicity, subsequent infusions can be administered over a planned infusion time of 90 minutes, with \sim 20% of the total dose administered in the first 30 minutes and the remaining 80% of the total protein dose administered in the subsequent 60 minutes (Dakhil 2014, Genentech 2016).

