6.8.3.3. Management of Rituximab Infusion Toxicity

Rituximab can cause severe, including fatal, infusion reactions (Genentech 2016). Patients with pre-existing cardiac or pulmonary conditions, those who experienced prior cardiopulmonary adverse reactions to rituximab, and those with high numbers of circulating malignant cells ($\geq 25 \times 10^9 / L$) may be at particular risk. Severe reactions typically occur during the first infusion and are generally less frequent and less severe with subsequent infusions. The time to onset of infusion toxicity ranges from 30 to 120 minutes. Rituximab-induced infusion reactions and sequelae include urticaria, hypotension, angioedema, hypoxia, bronchospasm, pulmonary infiltrates, acute respiratory distress syndrome, myocardial infarction, ventricular fibrillation, cardiogenic shock, and/or anaphylactoid events.

Version 9, 18 Feb 2020

Rituximab infusions should be interrupted or slowed in subjects experiencing Grade ≥ 3 rituximab-related infusion reactions. Medical management (eg, oxygen, epinephrine, bronchodilators, and/or glucocorticoids) should be instituted, as needed. Upon improvement of symptoms, the infusion may be continued at 50% of the previous rate. At the discretion of the investigator, rituximab therapy may be permanently discontinued in subjects with Grade 4 infusion reactions or with reactions requiring substantial intervention.

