6.8.4.3. Management of Atezolizumab Infusion Toxicity

While infrequent (incident <2%), severe infusion reactions have occurred in clinical trial subjects receiving atezolizumab. For subjects with Grade 1 or 2 infusion reactions, the atezolizumab infusion should be interrupted or slowed. For subjects with Grade \geq 3 infusion reactions, atezolizumab therapy should be permanently discontinued.

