6.8.3.3 Management of Rituximab Infusion/Injection Toxicity

Rituximab can cause severe, including fatal, infusion reactions (Genentech 2016). Patients with pre-existing cardiac or pulmonary conditions, those who experienced prior cardiopulmonary adverse reactions to rituximab, and those with high numbers of circulating malignant cells (≥25 x 10⁹/L) may be at particular risk. Severe reactions typically occur during the first infusion and are generally less frequent and less severe with subsequent infusions. The time to onset of infusion toxicity ranges from 30 to 120 minutes. Rituximab-induced infusion reactions and sequelae include urticaria, hypotension, angioedema, hypoxia, bronchospasm, pulmonary infiltrates, acute respiratory distress syndrome, myocardial infarction, ventricular fibrillation, cardiogenic shock, and/or anaphylactoid events.

Rituximab infusions/injections should be interrupted or slowed in subjects experiencing Grade ≥3 rituximab-related infusion reactions. Medical management (eg, oxygen, epinephrine, bronchodilators, and/or glucocorticoids) should be instituted, as needed. Upon improvement of symptoms, the infusion may be continued at 50% of the previous rate. At the discretion of the investigator, rituximab therapy may be permanently discontinued in subjects with Grade 4 infusion/injection reactions or with reactions requiring substantial intervention.

Clinical Study Report 16.1 Study Information Protocol: LAM-002A-NHL-CLN01

Version 9, 18 Feb 2020

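### A subject with a Grade 3 reaction to the first rituximab infusion may still be given the faster 90-minute infusion next time

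*Combined protocol and SAP*

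**What the plan says.** Section 6.8.3.2 (Rituximab Administration) gives two ways to run intravenous infusions after the first. The standard one starts at 100 mg/hour and rises by 100 mg/hour every 30 minutes, provided there is no infusion toxicity, up to 400 mg/hour. The alternative is shorter: "subsequent infusions can be administered over a planned infusion time of 90 minutes", with about 20% of the dose in the first 30 minutes and 80% in the next 60. It is available "for subjects who tolerate the first infusion with Grade \leq 3 infusion toxicity".

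Section 6.8.3.3 (Management of Rituximab Infusion/Injection Toxicity) says: "Rituximab infusions/injections should be interrupted or slowed in subjects experiencing Grade ≥3 rituximab-related infusion reactions". Once symptoms improve, that infusion may go on at half its earlier rate. Permanent discontinuation is left to the investigator, for Grade 4 reactions or those needing substantial intervention. The section warns that reactions can be fatal, and adds: "The time to onset of infusion toxicity ranges from 30 to 120 minutes".

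Both rules appear in the Amendment 6 change record. Both appear again, as retained text, in the record of the later amendment that added subcutaneous rituximab.

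**The concern.** The two thresholds meet at Grade 3. A subject with such a reaction meets the criterion for interrupting or slowing the infusion and also the criterion for receiving the next one faster. The word for tolerating the infusion does not exclude this subject, because the sentence itself sets Grade 3 as an acceptable level of toxicity.

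No other rule shown closes the gap. The half-rate restart covers only the infusion under way, discontinuation after Grade 3 is discretionary, and Table 5 on rituximab modifications has no row for infusion reactions. A site that follows Section 6.8.3.2 literally could therefore speed up treatment after a severe reaction to a drug whose infusion reactions the protocol describes as sometimes fatal.

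The protocol is stricter with the other antibody. Under Section 6.8.4.3, for Grade 3 or higher "infusion reactions, atezolizumab therapy should be permanently discontinued". That is a different drug and does not set the rituximab limit, but it shows how seriously the same document takes this grade.

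**Working it through.** **Overlap of the rules.** Grades eligible for the 90-minute infusion: 3 or lower. Grades that call for interruption or slowing: 3 or higher. The common element is Grade 3. With an eligibility limit of Grade 2 the two sets have nothing in common.

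**Inputs.** From Section 6.8.3.2: dose 375 mg/m²; 90-minute schedule of 20% in 0.5 hour, then 80% in 1 hour; standard later infusions of 100, 200 and 300 mg/hour for 30 minutes each, then 400 mg/hour. BSA is not given in the documents; I assume 1.6 to 2.2 m².

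**Formulas.**
- Dose = 375 × BSA.
- First-phase rate = 0.20 × dose ÷ 0.5 h.
- Second-phase rate = 0.80 × dose ÷ 1 h.
- Standard duration: the first three steps deliver 50 + 100 + 150 = 300 mg in 90 minutes; the remainder takes (dose − 300) ÷ 400 hours.

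| BSA (m²) | Dose (mg) | First 30 min (mg/h) | Last 60 min (mg/h) | Last 60 min ÷ 400 | Standard duration (min) | Extra over 90 min |
|---|---|---|---|---|---|---|
| 1.6 | 600 | 240 | 480 | 1.20 | 135 | 45 |
| 1.8 | 675 | 270 | 540 | 1.35 | 146 | 56 |
| 2.2 | 825 | 330 | 660 | 1.65 | 169 | 79 |

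The first-phase rate stays below 400 mg/hour throughout this range. The second-phase rate passes 400 mg/hour when 0.8 × 375 × BSA > 400, that is, when BSA exceeds 400 ÷ 300 = 1.33 m².

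**Timing.** The fast phase runs from minute 30 to minute 90. If onset is counted from the start of the infusion, all of it lies within the 30 to 120 minutes that Section 6.8.3.3 gives for onset.

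**Who is exposed.** Eight intravenous treatments are planned, so at most 8 − 1 = 7 later infusions per subject. Subjects on the subcutaneous option receive only Cycle 1 Day 1 intravenously; their later treatments begin with "Three subcutaneous injections of 1,400 mg/23,400 Units", so the 90-minute rule does not reach them.

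**The case against.** The best counter-argument is that the two sections govern different moments. Section 6.8.3.3 manages the infusion in progress and Section 6.8.3.2 schedules the next one. The faster schedule is only an alternative, and the standard one is stated first. Section 6.8.3.3 also says severe reactions are generally rarer and milder at later infusions. Premedication precedes every dose, local practice may be followed, and a severe reaction during a 90-minute infusion would again lead to interruption or slowing. All of this is true, and it makes harm less likely. It does not explain why a severe reaction should leave a subject eligible for a faster rate. A general trend towards milder reactions is also weak reassurance for someone who has just had a severe one.

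A second objection is that the point rests on one inequality sign in text extracted from PDF, where such signs are not always reliable. If the page says below Grade 3, the conflict disappears. Two separate amendment texts show the same sign, which makes a misreading unlikely, but the page should be looked at. The Version 9 body is not in the part available, so its wording is inferred; the visible part of the latest change record lists no change to Section 6.8.3.

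Third, the excess over 400 mg/hour is a property of the 90-minute schedule for nearly everyone who receives it. It shows how fast the permitted infusion is, not how much risk is added by admitting Grade 3 subjects. That stands. So does the point that the sources cited for the 90-minute schedule were not available: the case for Grade 2 rests on consistency with Section 6.8.3.3, not on those sources.

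**Conclusion.** The concern holds. As written, a subject with a Grade 3 first-infusion reaction may receive later infusions on a schedule whose last hour runs at 1.2 to 1.65 times the standard maximum rate, for an assumed BSA of 1.6 to 2.2 m². The overlap itself needs no assumption beyond the printed grade limits. How many subjects it touches is unknown, because the documents give no rate of Grade 3 first reactions; the number is probably small, and the extension stage is limited to fewer than four subjects. This is a subject-safety matter with no bearing on the statistical analysis. It should be corrected because the possible harm is serious and the correction is trivial.

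**What to change.** In Section 6.8.3.2, limit the 90-minute infusion to subjects whose first infusion caused no reaction above Grade 2. State that anyone with a Grade 3 first reaction who continues intravenous rituximab uses the standard later-infusion schedule, from 100 mg/hour to at most 400 mg/hour. Keep the Grade 3 threshold for interruption or slowing in Section 6.8.3.3; raising it would also remove the overlap, but at the expense of safety. Check the sign in the Version 9 body when making the edit, and carry the change into the site infusion orders.

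The cost is one threshold, one added sentence and updated orders. Each affected infusion takes about 135 to 169 minutes instead of 90, assuming standard escalation without toxicity, for at most seven infusions per subject. No endpoint, sample size or analysis changes.
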